5.3 Schematic diagram

Figure 5-1 presents a schematic diagram of the LCM dosing and taper schedule for subjects <50kg receiving the oral solution formulation, and Figure 5-2 presents a schematic diagram of the LCM dosing and taper schedule for subjects ≥ 50 kg receiving the oral solution or tablet formulation.

REDACTED COPY

This document cannot be used to support any marketing authorization application and any extensions or variations thereof.

Figure 5-1: Schematic diagram - LCM dosing and taper schedule for subjects <50kg receiving oral solution formulation

[figure not shown]
[figure not shown]

Figure 5-2: Schematic diagram - LCM dosing and taper schedule for subjects ≥50kg receiving oral solution or tablet formulation

TC=Telephone Contact; V=Visit

Note: LCM dosing is designated as “mg/day”

^a During Titration Period dosage may be adjusted up or down based on investigator’s clinical judgment.

^b Dose reached at the end of Titration Period will be taken throughout Maintenance Period. Subjects may be eligible for participation in the additional open-label study (SP848) if they have completed the Maintenance Period and are taking a minimum dose of 200mg/day (tablets/oral solution). Subjects will begin SP848 on the LCM dose they achieved in the Maintenance Period in SP0966. Subjects who do not complete the full 12 weeks of the Maintenance Period may still be eligible to enter the SP848 open-label study after consultation with the medical monitor.

^c Subjects with doses <150mg/day do not need to taper. See Table 7-5 for exact taper schedule. Taper is not required for subjects participating in the additional open-label study (SP848). A slower or faster taper is permitted if medically necessary. Taper of LCM may not be required for some subjects who discontinue study medication prematurely, depending on the treatment option selected by the investigator in consultation with the subject and/or parent/legal representative. The Taper Period is followed by a Safety Follow-Up Visit 2 weeks (±2 days) after the final dose of LCM and a Safety Follow-Up Telephone Contact 30 days (-1/+3 days) after the final dose of LCM.

5.4 Rationale for study design and selection of dose

Epilepsy is a condition for which an improved benefit/risk ratio for medicinal products remains a challenge; this is especially true for pediatric patients. Based on the demonstrated efficacy and safety of LCM as adjunctive treatment in adult subjects with partial-onset seizures, and the experience with other AEDs in pediatric subjects, it is expected that LCM will also exhibit an acceptable benefit/risk profile in the pediatric population with uncontrolled generalized seizures.

In this study, the safety and tolerability of LCM will be studied when added to 1 to 3 concomitant AEDs in pediatric subjects with epilepsy syndromes associated with generalized seizures. The study will also obtain preliminary efficacy data of LCM on seizure frequency in pediatric epilepsy syndromes associated with generalized seizures.

This study is an exploratory study to investigate on which syndromes LCM has a beneficial effect in order to plan confirmatory study(ies) and exclude syndromes for which LCM has no clear benefit or possibly induces exacerbations.

Based on the currently available LCM pediatric safety and PK data from SP847 and SP1047, as well as on information available in the medical literature, the dosing recommendations for SP0966 are as follows:

- Lacosamide dosing should aim to achieve LCM plasma concentrations equivalent to the average steady-state LCM plasma concentration reached after a LCM 200 to 600mg/day dose administration in adult studies.
- A weight-based flexible dosing scheme is recommended:
 - Subjects <50kg: LCM 4-12mg/kg/day (oral solution)
 - Subjects ≥50kg: LCM 200 to 600mg/day (tablets/oral solution)

6 SELECTION AND WITHDRAWAL OF SUBJECTS

6.1 Inclusion criteria

To be eligible to participate in this study, all of the following criteria must be met:

1. A signed informed consent has been obtained from the parent/legal representative and assent has been obtained from the subject (when possible or as required according to local Institutional Review Boards [IRBs]/Independent Ethics Committees [IECs]).
2. Subject and/or caregiver (which may be a parent, a legal representative, or other caregiver) are willing and able to comply with all study requirements including maintaining a daily seizure diary.
3. Subject is male or female, ≥1 month to <18 years of age. For preterm infants <1 year old, the corrected gestational age should be used when determining eligibility. The generally accepted definition of corrected gestational age, which is calculated by subtracting the number of weeks born before 37 weeks of gestation from the chronological age, will be used for this study.

4. Subject has a diagnosis of uncontrolled epilepsy with generalized seizures (Type II) according to the International Classification of Epileptic Seizures (1981) (see Section 17.1). The underlying epilepsy syndrome should be documented. Diagnosis should have been established by clinical history and an EEG with generalized spike-wave discharges. Documentation of the EEG finding of generalized spike waves (EEG recording or a report) is required. The EEG should have been performed no more than 18 months prior to Visit 1 (with no change to diagnosis or seizure types during this time).
5. Subject must have experienced 2 or more events (typical generalized seizures associated with diagnosed epilepsy syndrome) within the 6-week prospective Baseline Period.
6. Subject is on a stable dosage regimen of 1 to 3 AEDs. The daily dosage regimen of concomitant AED therapy must be kept constant for a period of at least 4 weeks prior to the Baseline Period.
7. Vagal nerve stimulation is allowed and will not be counted as a concomitant AED. The VNS device must be implanted for at least 6 months before Visit 1 and the device settings must be stable for at least 4 weeks before Visit 1 and be kept stable during the Baseline Period and the Treatment Period. Use of the VNS device magnet is allowed.
8. Body weight at Visit 1 is at least 4kg for infants.
9. Females of childbearing potential must have a negative pregnancy test at Visit 1.
10. Subjects with West Syndrome are eligible if Baseline EEG demonstrates hypsarrhythmia despite treatment with at least 2 AEDs appropriate for the treatment of this syndrome.

6.2 Exclusion criteria

Subjects are not permitted to enroll in the study if any of the following criteria are met:

1. Subject has previously participated in this study, subject has been assigned to LCM in a previous LCM study, or subject has ever received LCM.
2. Subject is currently participating or has participated within the last 2 months in any study of an investigational drug or experimental device.
3. Subject has a history of convulsive status epilepticus within 1 month prior to Visit 1.
4. Subject has a current or previous diagnosis of pseudoseizures, conversion disorders, or other nonepileptic ictal events that could be confused with seizures.
5. Subject has exclusively typical absence (Type IIA1) or atypical absence (Type IIA2) seizures (no other generalized seizure types are reported), or has only partial-onset seizures (Type I).
6. Subject has primary generalized tonic-clonic seizures with a diagnosis of idiopathic generalized epilepsy.
7. Subject has any medical or psychiatric condition that, in the opinion of the investigator, could jeopardize the subject's health or would compromise the subject's ability to participate in this study.

8. Subject ≥ 6 years of age has a lifetime history of suicide attempt (including an actual attempt, interrupted attempt, or aborted attempt), or has suicidal ideation in the past 6 months as indicated by a positive response (“Yes”) to either Question 4 or Question 5 of the Columbia Suicide Severity Rating Scale (C-SSRS) at Screening.
9. Subject has a known hypersensitivity to any components of the investigational medicinal product (IMP).
10. Subject has a medical condition that could reasonably be expected to interfere with drug absorption, distribution, metabolism, or excretion.
11. Subject has a known history of severe anaphylactic reaction or serious blood dyscrasias.
12. Subject has any history of alcohol or drug abuse within the previous 2 years.
13. Subject has an acute or sub-acutely progressive central nervous system disease. Subject has epilepsy secondary to a progressing cerebral disease or any other progressively neurodegenerative disease (malignant brain tumor or Rasmussen Syndrome).
14. Subject has alanine aminotransferase (ALT), aspartate aminotransferase (AST), or total bilirubin levels $\geq 2x$ the upper limit of normal (ULN) or has alkaline phosphatase levels $\geq 3x$ ULN.
15. Subject has impaired renal function (ie, creatinine clearance is lower than 30mL/min) at Visit 1.
16. Subject has sick sinus syndrome without a pacemaker, or second- or third-degree atrioventricular (AV) block.
17. Subject has a clinically relevant ECG abnormality, in the opinion of the principal investigator (ie, second- or third-degree heart block or a corrected QT interval [QTc] greater than 450ms).
18. Subject has hemodynamically significant heart disease (eg, heart failure).
19. Subject has an arrhythmic heart condition requiring medical therapy.
20. Subject has a known cardiac sodium channelopathy, such as Brugada syndrome.
21. Female subject who is pregnant or nursing, and/or a female subject of childbearing potential who is not surgically sterile or does not practice 1 highly effective method of contraception (according to International Conference on Harmonisation [ICH] guidance defined as those that result in a failure rate of less than 1% per year when used consistently and correctly), unless sexually abstinent, for the duration of the study. Female subject of childbearing potential taking enzyme inducing antiepileptic drugs (EI AEDs) (carbamazepine, phenytoin, barbiturates, primidone, topiramate, oxcarbazepine) who is not surgically sterile or does not practice 1 highly effective method of contraception according to the World Health Organization recommendation (ie, depot medroxyprogesterone acetate, norethisterone enantate, intrauterine devices, combined injectables, and progestogen implants) with administration of EI-AEDs or does not practice 2 combined methods of contraception (ie, combined hormonal contraception plus

barrier method with spermicidal agent), unless sexually abstinent, for the duration of the study.

22. Subject has been treated with vigabatrin and experienced any vision loss. Subjects who have received vigabatrin in the past must have documentation of an assessment for vision loss prior to study entry or documentation of why visual field testing cannot be performed.
23. Subject has been treated with felbamate and has experienced any serious toxicity issues (defined as liver failure, aplastic anemia) with this treatment. Subjects treated with felbamate for less than 12 months are excluded. Note: any subject who has been treated with felbamate for at least 12 months and has not experienced serious toxicity issues is eligible.
24. Subject is taking monoamine oxidase (MAO) inhibitors or narcotic analgesics.
25. Subject is on a ketogenic or other specialized diet. If he/she was on a specialized diet in the past, he/she must be off the diet for at least 2 months prior to the Screening Visit (Visit 1).

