5.1.2 Planned number of subjects and site(s)

Approximately 50 subjects will be enrolled. It is planned to enroll approximately 40 subjects between 4 years and <18 years of age and at least 10 subjects between 1 month and <4 years of age.

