11.6 Laboratory measurements

Blood and urine specimens for routine assay of hematology, clinical chemistry, and urinalysis testing will be collected according to the tabular schedule of study procedures, Section 5.2. Urinalysis will be performed for subjects aged 5 to 17 years only. A central laboratory will perform the routine analysis of blood and urine specimens. Pregnancy testing will also be performed (see Section 11.6.3). The procedures for handling and shipping these specimens will be provided to the sites.

The laboratory tests to be performed are presented in Table 11–2.

Table 11–2 Laboratory measurements

Hematology	Chemistry	Urinalysis
RBC count WBC count Differential count Platelet count Hematocrit Hemoglobin	Calcium Serum electrolytes (sodium, potassium, chloride, bicarbonate) Total serum protein Albumin Phosphorus Glucose Uric acid Alkaline phosphatase BUN Creatinine AST ALT GGT Total bilirubin Cholesterol Triglycerides	Albumin Specific gravity Ketones Glucose pH Microscopic exam for blood cells or casts/high power field

ALT=alanine aminotransferase; AST=aspartate aminotransferase; BUN=blood urea nitrogen; GGT=gamma-glutamyltransferase; RBC=red blood cell; WBC=white blood cell

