A total of 50 evaluable subjects are planned for enrollment for this study across 2 age **groups**. The first **age group** will consist of approximately 40 subjects between 4 years and <18 years of age. The second **age group** will consist of at least 10 subjects between 1 month and <4 years of age. Since the primary objective of this open-label exploratory study is to assess the safety and preliminary efficacy of LCM in subjects with generalized seizures and other epilepsy syndromes, a sample size of 50 evaluable subjects is deemed adequate for meeting the objectives of the study. No formal sample size calculations were performed.

Change #58

Section 16 REFERENCES

The following citations have been added:

Institute of Medicine. **Epilepsy across the spectrum: promoting health and understanding**. Washington, DC: The National Academies Press; 2012.

17.5 Protocol Amendment 4

Rationale for the amendment

The present amendment has been issued to open enrollment of subjects ≥ 1 month to <2 years of age in SP0966. A weight-based dosing scheme has been established for pediatric subjects down to ≥ 1 month of age, which is consistent with the current SP0966 dosing scheme. This dosing scheme is based on safety and PK modeling using data from previous pediatric and adults studies.

In addition, the exclusion of subjects with primary generalized tonic-clonic seizures (PGTCS) with a diagnosis of idiopathic generalized epilepsy (IGE) from the SP0966 study population is removed in this amendment. In the original SP0966 protocol dated 30 May 2012, these

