The present amendment has been issued to exclude subjects with primary generalized tonic-clonic seizures with a diagnosis of idiopathic generalized epilepsy from the SP0966 study population. A confirmatory study (SP0982) to investigate the effect of LCM in this population is being conducted and, therefore, this population will not be included in SP0966.

As per the recommendations made by the USA FDA, the creatinine clearance has been changed from less than 50mL/min to less than 30mL/min.

In addition, minor administrative changes and edits were made.

Modifications and changes

Global changes

The following key changes were made throughout the protocol:

- Subjects with primary generalized tonic-clonic seizures with a diagnosis of idiopathic generalized epilepsy were excluded from the study population.
- Exclusion criterion for creatinine clearance rate has changed from <50mL/min to <30mL/min.
- Exclusion criterion number 20 has been reworded to clarify that the excluded sodium channelopathies are cardiac.
- Administrative changes: the name of the Study Physician and the name of the CRO have been updated, and the Sponsor Declaration has been updated for electronic signature.
- Russia has been removed as a participating country.

Specific changes

Change #1

SPONSOR DECLARATION

SPONSOR DECLARATION

I confirm that I have carefully read and understand this protocol and agree to conduct this clinical study as outlined in this protocol and according to current Good Clinical Practice.

Clinical Project Manager

[REDACTED]

Date/Signature

Clinical Trial Biostatistician

[REDACTED], MA

Date/Signature

Study Physician

[REDACTED], MD

Date/Signature

Clinical Program Director

[REDACTED], BS

Date/Signature

Has been revised and moved to Section 19:

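### Exclusion criterion 15 sets an absolute renal cut-off of 30 mL/min for all ages; read literally, it bars young infants with normal kidneys whom the protocol was amended to admit

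*Protocol*

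**What the plan says.** Protocol Section 6.2 opens with a hard rule: "Subjects are not permitted to enroll in the study if any of the following criteria are met". Criterion 15 under it reads: "Subject has impaired renal function (ie, creatinine clearance is lower than 30mL/min) at Visit 1". The abbreviation inside the bracket makes the figure the definition of impairment, not an example of it. The criterion has no body-surface-area term, no age band and no exemption for infants.

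The entry criteria in Section 6.1 reach down to very small children. Criterion 3 says "Subject is male or female, ≥1 month to <18 years of age", and criterion 8 says "Body weight at Visit 1 is at least 4kg for infants". Section 5.1.2 plans "at least 10 subjects between 1 month and <4 years of age". Amendment 4 (Section 17.5) gives its purpose as follows: "The present amendment has been issued to open enrollment of subjects ≥ 1 month to <2 years of age in SP0966".

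The current figure comes from Amendment 5 (Section 17.6), which cites an FDA recommendation: "the creatinine clearance has been changed from less than 50mL/min to less than 30mL/min". The number moved and the unit did not.

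Neither the protocol nor the SAP says how clearance is to be obtained. Table 11–2 lists creatinine but not creatinine clearance. On urine, Section 11.6 says "Urinalysis will be performed for subjects aged 5 to 17 years only", so no scheduled sample supports a measured clearance in the youngest children. For them the value has to be an estimate, by a method left to the site.

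**The concern.** A clearance in mL/min measures the output of the whole body. A healthy small child therefore has a low value for the same reason that the child has a small body surface. One absolute limit marks poor function in an adult-sized adolescent and lies above normal function in a young infant.

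Two things are at stake. First, a site that applies the criterion as written turns away infants with healthy kidneys. That undoes much of Amendment 4 and thins the data for parts of the plan that depend on the youngest children: the pharmacokinetic objective from 1 month of age, the Bayley-III assessment below 18 months, and possibly the infantile spasms/West syndrome subgroup, which the SAP (Section 4.8) presents only if it has at least 4 subjects. Second, a site that uses an estimate already expressed per 1.73 m² could enrol the same infant. Eligibility in the youngest children would then depend on the site's formula and not on the child's kidneys.

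**Working it through.** The plan derives no figure here: 30 mL/min is a stated threshold and no sample-size calculation was made. The check is a unit conversion.

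**Inputs from the documents:** cut-off 30 mL/min (Section 6.2), minimum infant weight 4 kg and lower age limit 1 month (Section 6.1).

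**Assumptions, not in the documents:** typical weights and heights by age, the body-surface-area (BSA) formulas, and normal clearance ranges.

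**Formulas** (W in kg, H in cm):
- BSA = √(W × H / 3600) (Mosteller), cross-checked with BSA = (4W + 7)/(W + 90)
- normalised clearance needed to reach 30 mL/min = 30 × 1.73 / BSA = 51.9 / BSA
- absolute clearance = normalised clearance × BSA / 1.73

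**Step 1: what a child must have in order to pass.** At 4 kg and 54 cm, BSA = √(4 × 54 / 3600) = 0.245 m², and 51.9 / 0.245 = 212 mL/min/1.73 m².

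| Weight / height (assumed) | Normalised clearance needed (mL/min/1.73 m²) |
|---|---|
| 4 kg / 54 cm | 212 |
| 8 kg / 69 cm | 133 |
| 10 kg / 76 cm | 113 |
| 12 kg / 87 cm | 96 |
| 16 kg / 102 cm | 77 |
| 50 kg / 160 cm | 35 |

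Over the weights below 4 years, the second BSA formula agrees within about 2%.

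**Step 2: what a child with normal kidneys has.** Absolute clearance uses the mean of the two BSA values.

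| Age (assumed weight) | Assumed normal range, low–mid–high (mL/min/1.73 m²) | Absolute clearance (mL/min) | Against 30 |
|---|---|---|---|
| 1 month (4 kg) | 30–50–70 | 4.2–7.0–9.9 | all below |
| 3 months (6 kg) | 45–65–90 | 8.3–12.1–16.7 | all below |
| 6 months (7.7 kg) | 60–80–110 | 13.3–17.7–24.3 | all below |
| 9 months (8.9 kg) | 65–88–120 | 16.0–21.7–29.6 | all below, the top value only just |
| 12 months (9.8 kg) | 70–95–130 | 18.6–25.2–34.5 | midpoint below, top above |
| 18 months (11 kg) | 80–105–140 | 23.2–30.5–40.7 | midpoint just above |
| 24 months (12.2 kg) | 90–115–150 | 28.3–36.2–47.2 | only the low end below |
| 36 months (14.3 kg) | 90–120–150 | 32.0–42.7–53.3 | all above |
| 47 months (16.2 kg) | 90–120–150 | 35.2–46.9–58.7 | all above |

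**Step 3: break-even weight.** Setting absolute clearance to 30 mL/min in the second formula gives 8.9 kg for a child at 120 mL/min/1.73 m², 11.4 kg at 100 and 13.1 kg at 90.

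**The case against.** The strongest reply is that the harm is conditional. The criterion is aimed at impaired function, the protocol plainly means to enrol infants, and no method is prescribed. A site using a paediatric estimate per 1.73 m² would meet no difficulty. That is fair: the documents do not show which reading sites adopted, so one cannot conclude that infants were in fact turned away. But the reply works only by departing from the written unit, and it leaves two sites free to classify one infant in opposite ways.

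A reader might also infer that the group of at least 10 subjects aged 1 month to under 4 years cannot be recruited. The documents do not support that. The group has no sub-quota below 2 years, and typical 2- and 3-year-olds pass. Nor can one say that toddlers in general are excluded, or that every child under 10 kg is: at 12 months the upper part of the assumed range passes.

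Two further points stand. The FDA recommendation behind the figure is not reproduced, so its intended unit is unknown. And the study is exploratory and descriptive, so the flaw affects who is enrolled and does not invalidate a planned analysis. Neither point removes the conflict between the criterion and the entry criteria.

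**Conclusion.** The concern holds with a limited scope. Criterion 15 is wrong as written for young infants, because the text gives a definite rule and that rule contradicts inclusion criteria 3 and 8 and the purpose of Amendment 4. The conflict is near-total up to about 9 months, partial from roughly 12 to 24 months, and absent for typical children from about 2 years. The 1-month-to-under-2-years range is therefore largely, not wholly, closed under a literal reading.

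The absolute unit and the lack of a method are read directly from the documents. The age boundaries rest on the assumed body sizes and normal ranges, and would shift somewhat with other assumptions. The result at the 4 kg entry weight is not sensitive to them: the 212 needed is about three times the highest assumed 1-month value of 70.

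**What to change.** Reconcile criterion 15 with the 1-month and 4 kg entry criteria. Express it in mL/min/1.73 m² and require the value to be calculated the same way for every subject, from Visit 1 creatinine and height, with one named paediatric equation. Having the central laboratory report the value would remove site variation. The sponsor should confirm the numerical cut-off in the new unit, including whether it suits the youngest infants; no value is proposed here.

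That decision should not be treated as a formality. Purely to show the effect of the unit, the present 30 read per 1.73 m² would correspond to about 4.2 mL/min absolute at 4 kg, 8.0 at 9.8 kg and 11.7 at 16.2 kg, and the lowest assumed 1-month value (30) would sit exactly on the limit.

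The cost is a short amendment plus the sponsor's decision on the cut-off. No new procedure is needed, because creatinine (in clinical chemistry) and height are already collected at Visit 1 (Sections 8.1.1 and 11.6). Eligibility would change mainly for the smallest infants, and for a few larger adolescents near the limit.
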